### **Conclusion:**

1. According to the NRI nutritional status assessment scales, the SGA mixed type of nutritional support at the time of transfer of patients to the specialized department and upon completion of this area of intensive therapy in the specialized department by 12-15 days of the postoperative period showed higher effectiveness in stabilizing the condition and maintaining the patients' caloric intake in a comparative aspect with the group of isolated enteral nutrition and parenteral nutrition.
2. Throughout the entire period of isolated enteral, parenteral and mixed nutritional support, all patients (100%) showed a relatively constant level of total blood protein.
3. In patients of all three groups, throughout the entire period of nutritional support, fluctuations in the level of basal metabolism were observed, which was due to the variability of body mass index and the dynamics of the temperature curve after surgery. In patients in the groups with enteral and parenteral nutrition, by the end of nutritional support (days 15-20), the level of basal metabolism was observed to approach its initial values. With a mixed type of nutrition, a statistically significant decrease in the level of basal metabolic rate was observed, which suggests a more effective coverage of the energy costs of patients with this option of replenishing nutritional ingredients.

**Researcher:** [name], PhD student KSMU

[contact].

e-mail: [contact].

[figure not shown]
Signature  17.03.2020

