## **1. Methods and procedures.**

At the first stage, modern ideas about methods for assessing nutritional status and methods of nutritional support in the early postoperative period of patients operated on for malignant tumors of the hepatopancreatoduodenal zone were studied.

At the second stage, taking into account the need to select the optimal method of nutritional support in the early postoperative period, patients underwent an intragroup and intergroup comparative analysis of the main clinical and laboratory indicators, reflecting the most satisfactory dynamics of plastic processes regarding the type of nutritional support: enteral, parenteral and mixed.

To solve these problems, a prospective, longitudinal, parallel study and retrospective analysis of the results of treatment of 91 patients with malignant tumors of the hepatopancreatoduodenal zone who underwent the following operations were carried out:

- 1) resection of various segments of the liver;
- 2) hemihepatectomy;
- 3) transhepatic drainage of the right and left hepatic duct;
- 4) bypass gastroenteroanastomosis or cholecystoenteroanastomosis with interintestinal enteroenteroanastomosis according to Brown;
- 5) gastro-pancreatoduodenal resection;
- 6) corporecaudal resection of the pancreas with splenectomy.

The study was carried out on the basis of the KGP at the RVC "Multidisciplinary Hospital No. 3 of the city of Karaganda". Venue: intensive care unit.

To identify nutritional deficiencies, there are screening methods recommended by the international clinical nutrition associations ASPEN (American Society for Parenteral and Enteral Nutrition - ASPEN) and ESPEN (European Society for Parenteral and Enteral Nutrition - ESPEN), including questioning patients, using standard anthropometric and laboratory data, which makes it possible to assess nutritional status and the degree of its impairment.

At the first stage, the clinical condition of the patient was assessed using the Nutritional Risk Screening (NRS, 2002), Subjective Global Assessment (SGA) and Nutritional Risk Index (NRI) protocols before surgery and on the 5th, 10th, 15th day after surgery .

A comparative assessment of the clinical effectiveness of the use of types of nutritional nutrition in a complex of therapeutic measures after these operations in the hepatopancreatoduodenal zone was carried out.

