## **Methods of statistical data analysis**

All patients hospitalized for special treatment with a verified diagnosis of a malignant neoplasm were subjected to the study in the abdominal department of the KGP at the Regional Oncological Dispensary, Karaganda.

The quantitative and qualitative indicators obtained during the study were analyzed using descriptive and analytical statistics methods. For statistical processing of qualitative (diagnosis codes, dichotomous data) and quantitative variables: symptom intensity, severity, frequency of occurrence, we used the calculation of the median level (Me) with 25%-75% quartiles (Q25; Q75) and the calculation of the arithmetic mean (M) with error (m) and 95% confidence interval (95% CI), standard deviation (s). Quantitative variables were checked for normality of distribution using the Kolmogorov-Smirnov test, as well as the module of Skewness and Kurtosis for quantitative variables  $| \leq 2 |$ . Differences in the 3 groups of patients for quantitative variables corresponding to a normal distribution were identified using the Student's t test for unrelated groups, first for 3 or more groups, and then in pairs for each pair using the Student's t test. Differences for rank variables, or quantitative but not normally distributed for unrelated groups, were determined by the Kruskal-Wallis test or median test for 3 groups, and then pairwise or non-parametric Mann-Whitney test for each of the 3 pairs (groups 1 and 2, groups 1 and 3, groups 2 and 3), and for related groups (dynamic observations) by the Kendall test for 3 groups and then by the Wilcoxon test (Wilcoxon) for each of the 3 pairs (baseline, after 5 days and after 10 days).

Correlation was performed for quantitative variables according to Pearson and for rank variables according to Spearman. Statistical processing of the results was carried out using the Statistica program version 10.

**Results and discussion.** The nutritional status of patients in all three groups before surgery and during the 10-12 days of the postoperative period according to the methods of assessing nutritional status NRS, SGA and NRI was assessed as normal, moderate and severe malnutrition

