As can be seen from the presented data, in the preoperative period, according to the SGA assessment, 24 patients in the enteral group, 19 patients in the parenteral group, and 17 patients in the mixed group had normal nutritional status before surgery, with variations relative to patients with moderate to severe malnutrition. Assessment of nutritional status before surgery using the NRI scale allowed us to confirm the nutritional status of the vast majority of patients in all groups as relatively normal

Thus, in 62 of the 91 patients examined, the NRI was assessed as true negative (normal nutritional status), in 26 as true positive (moderate malnutrition), and in 3 as severe malnutrition. Data from the NRI method during this time period had a strong correlation with the results of the SGA scale ( $p < 0.005$ ).

On the 10-12th day of the postoperative period in patients of the “enteral” group, the results of the assessment on the SGA scale remained unchanged; according to the NRI rating scale, there was an increase in “moderate malnutrition” per patient (25%).

With parenteral nutritional support, 17 patients had “normal nutrition”, 14 patients had moderate malnutrition, with regression of “severe malnutrition” in 1 patient. In the mixed nutrition group, there was a complete elimination of signs of “severe malnutrition” by 100% according to the given scales ( $p < 0.005$ ).

In patients of all study groups, throughout the entire period of nutritional support, fluctuations in the level of basal metabolism were observed in average values of  $335.89 \pm 53.6$  kcal/day (13.44%) from the initial value - 1-2 days of the postoperative period and were due to variability body mass index and the dynamics of the temperature curve after surgery.

In patients in the groups with enteral and parenteral nutrition, by the end of these types of energy subsidies (days 10-15), the level of basal metabolism was observed to approach its initial values -  $2500.1 \pm 353.4$  kcal/day and  $2350.0 \pm 330.5$  kcal/day days accordingly. With a mixed type of nutrition, there was a statistically significant decrease in the level of basal metabolism by 6.78% ( $2250.0 \pm 105.2$  kcal/s), which allows us to conclude that patients' energy costs are more effectively covered with this option of nutritional support in a comparative aspect with isolated types nutrition ( $p < 0.03$ ).

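### Conclusion item 1 ranks mixed nutrition first on NRI and SGA alone, although three unranked scales were planned and no reason is given for leaving out NRS

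*Combined protocol and SAP*

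**What the plan says.** Protocol section III.1 (Methods and procedures) states that the patient's condition was "assessed using the Nutritional Risk Screening (NRS, 2002), Subjective Global Assessment (SGA) and Nutritional Risk Index (NRI) protocols", before surgery and on postoperative days 5, 10 and 15. The report repeats this under Clinical research program. Neither place names a primary scale or an order among the three. The statistical sections (protocol III.2 and the report's Methods of statistical data analysis) give no primary scale, hierarchy or multiplicity rule.

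The opening sentence of Results and discussion keeps all three: nutritional status before surgery and over 10-12 postoperative days "according to the methods of assessing nutritional status NRS, SGA and NRI was assessed as normal, moderate and severe malnutrition".

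The results that follow carry these scale labels:

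- **SGA, baseline:** "according to the SGA assessment, 24 patients in the enteral group, 19 patients in the parenteral group, and 17 patients in the mixed group" were normal.
- **NRI, baseline:** "in 62 of the 91 patients examined, the NRI was assessed as true negative (normal nutritional status), in 26 as true positive" (moderate malnutrition), with 3 severe.
- **NRI against SGA:** "Data from the NRI method during this time period had a strong correlation with the results of the SGA scale", with p<0.005 and no coefficient.
- **Enteral arm, days 10-12:** "the results of the assessment on the SGA scale remained unchanged; according to the NRI rating scale, there was an increase" in moderate malnutrition.

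The parenteral follow-up counts name no scale. The mixed-arm follow-up statement refers to the scales given, without saying which.

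Conclusion item 1 begins "According to the NRI nutritional status assessment scales, the SGA mixed type of nutritional support" and goes on to call mixed support more effective than either isolated method, at transfer to the specialized department and at completion by days 12-15.

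**The concern.** Objective 1 asks for a comparison of nutritional status between the three feeding methods, and Conclusion item 1 is the report's answer. Three instruments were planned for that purpose on equal footing. When a claim that one arm is better rests on two of them and is silent on the third, the reader of the conclusion cannot tell whether the third agrees, disagrees or was never analysed. If the scales that carry a conclusion depend on what they showed, the conclusion leans towards finding a difference. Nothing set in advance explains why NRI and SGA should carry this one.

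The choice of scale can matter here. In the enteral arm at days 10-12 the two reported scales already part company: SGA did not change, while NRI showed more moderate malnutrition.

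**Working it through.** No sample-size or power formula applies. The check is to follow each scale from plan to conclusion and to confirm that the labelled counts are coherent.

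**Step 1. Do the labelled counts add up?**
- NRI at baseline: 62 + 26 + 3 = 91, the study total (31 + 30 + 30 = 91). The report's own figure is reproduced.
- SGA normal at baseline: 24 + 19 + 17 = 60 of 91. By arm this is 24/31 = 77%, 19/30 = 63% and 17/30 = 57%.

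Both scales were therefore tabulated in some form.

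**Step 2. Trace each scale.**

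| Stage | NRS 2002 | SGA | NRI |
|---|---|---|---|
| Planned (protocol III.1; report, Clinical research program) | yes | yes | yes |
| Opening sentence of the results | yes | yes | yes |
| Labelled baseline result | none | yes, by arm (normal only) | yes, arms pooled |
| Labelled follow-up result | none | enteral arm, days 10-12 | enteral arm, days 10-12 |
| Named in Conclusion item 1 | no | yes | yes |

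Three scales were planned, two have a labelled result, and the same two carry the conclusion.

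**Step 3. How much of the planned follow-up is attributed to a scale?** The plan implies 3 scales x 3 postoperative visits x 3 arms = 27 scale-visit-arm results. The readable text attributes two of them to a named scale: SGA and NRI in the enteral arm at days 10-12. None is for NRS, and none is for day 5 or day 15.

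**Step 4. Can NRS be recovered from the unlabelled statements?** The parenteral follow-up gives 17 normal and 14 moderate. These add to 31 in a group of 30, so they cannot be matched to any scale with confidence. The mixed-arm statement, that signs of severe malnutrition disappeared entirely, gives no count and no scale. Neither yields an NRS figure.

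**Step 5. Does the reported correlation stand in for NRS?** No. It relates NRI to SGA only, and a p-value without a coefficient does not show how closely even those two agree.

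**The case against.** The strongest reply is that the gap may lie in the extraction rather than in the report. The sentence introducing the three scales ends abruptly, the next paragraph refers to data presented to the reader, and no such display is in the text. NRS figures could be there. The mixed-arm statement about the scales given could also include NRS, since the results had just listed it. And the wording of Conclusion item 1 is garbled, so little should be read into which scale names it contains.

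Much of this stands. It rules out saying that NRS was never reported, and it limits the finding to the readable results text and the conclusion. It does not remove the point. The conclusion is intact as a sentence, it names two scales, and it gives no reason for leaving out the third. If a display does show NRS, the remedy becomes shorter but is still needed.

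It is also fair to say that adding NRS leaves other weaknesses of this conclusion in place. No between-group test on any scale is identified as the basis for the ranking. Scale results are reported at days 10-12, while the conclusion speaks of transfer and days 12-15.

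A reader might infer that NRS was dropped because it gave an unwelcome answer. The documents do not support that: nothing indicates what NRS showed, or when the choice of scales was made. A reader might also want to price the omission as a false-positive rate over all scales and visits. That would not measure this defect. It mixes visits with scales, it counts any single positive reading although the conclusion invokes two scales, and the documents state no significance level for it.

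**Conclusion.** The point holds in a limited form. Three unranked scales were planned. In the readable text only SGA and NRI have labelled results, and Conclusion item 1 claims that mixed nutrition is more effective on those two alone, without explanation. Its size is one planned scale of three missing from the main comparative claim. A numerical bias cannot be derived, because no primary scale, significance level or between-group result on any scale is given.

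The finding rests on the intact wording of the conclusion and on the absence of any NRS figure in the readable results. It does not assume that NRS is missing from a lost display, and it does not assert deliberate selection. Selective reporting is possible, not shown. Nor do the documents say that the three scales can replace one another, or that all three must point the same way before a claim is allowed. Such a unanimity rule would itself be added after the fact.

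**What to change.** 1. Report NRS by arm before surgery and on days 5, 10 and 15, in one table with SGA and NRI, each count labelled with its scale and visit. If NRS was not analysed, say so and why.
2. Compare the arms on all three scales with the between-group approach that the report already states for rank variables: Kruskal-Wallis across the three groups, then pairwise Mann-Whitney.
3. Reword Conclusion item 1 to give the result on NRS, SGA and NRI, and qualify the claim if they differ. If one scale is now named as primary, label that choice as post hoc.
4. If a display already shows NRS, cite it in the conclusion and state what it shows.

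The cost is some extra tabulation of data that the methods say were collected, and one reworded conclusion. No new measurement is needed. The downside for the authors is that the conclusion may become less favourable to mixed nutrition.

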## **I. Purpose of the study and introduction.**

**Purpose of the study.** Comparative analysis of the degree of influence of isolated enteral, isolated parenteral and mixed type of nutritional support on the nutritional status of cancer patients after operations performed in the hepatopancreatoduodenal zone in connection with malignant neoplasms in the early postoperative period.

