## **III. Methods and procedures**

Study plan:

- 1) Content analysis of medical documentation.

IV. 2) Obtaining informed consent;

- 3) Biochemical studies: transaminases, thymol test, urea, creatinine, study of total protein and its fraction, state of nitrogen metabolism, blood glucose level, body mass index
- 4) Study of the acid-base state and gas composition of the blood.
- 5) Control of tests before and in the early postoperative period against the background of ongoing nutritional support (determining quantitative ratios of fat mass, water and dry matter in patients before surgery and in the early postoperative period).
- 6) Determination of the immunological state before and after surgery as part of nutritional nutrition.

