Some nutritional status indicators available for determination at the Oncology Clinic were assessed - body mass index (weight measurements were carried out before surgery, on the 5th, 10th and 15th days), basal metabolic rate (calculated using the Harris-Benedict equation, based on anthropometric data of the patient (gender, age, weight and height).), laboratory parameters: blood hemoglobin, lymphocytes, total protein, serum albumin, serum transferrin, total bilirubin and direct, ALT, AST, which are related to the traditional method for assessing nutritional status.

Additionally, we assessed the duration of postoperative gastostasis, the timing of the onset of intestinal motility, the appearance of stool, the return to a normal diet, the length of patients' stay in the ICU, the readmission of patients to the ICU and the duration of the postoperative bed-day, and the incidence of complications was calculated.

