This fact was obviously associated with the preservation/restoration of parietal digestion in the gastrointestinal tract in the early postoperative period, despite postoperative intestinal paresis of varying degrees, and the involvement of nutrients in anabolic processes with parallel “covering” of the required daily caloric intake by parenteral administration of mixtures.

Evaluation and subsequent analysis of the results of laboratory examination in groups of patients in a comparative aspect showed a relatively slow and gradual decrease in the level of total blood protein by the 5th day of the postoperative period, on average, by  $6.8 \pm 0.95\%$  of the initial values, which,

apparently, was due to increased catabolism and ongoing protein losses (exudation, drainage, etc.) with a fairly significant increase by the end of nutritional support.

Thus, a statistically significant increase in the level of total blood protein was noted in the mixed nutrition group ( $p = 0.004$ ). In the groups with enteral and parenteral nutrition, differences in the dynamics of total protein levels were found at the level of a statistical trend:  $p=0.108$  and  $p=0.129$ , respectively.

When analyzing changes in the number of blood lymphocytes, it should be noted that before the operation the relative value of lymphocytes in the groups was significantly reduced ( $25.9\pm3.7\%$ ), but taking into account the methods and volumes of the operation, the tension of the cellular and humoral parts of the immune system, the dynamics of their level was expressed in the form of a statistically significant increase in the level of lymphocytes in the postoperative period by 10-12 days.

Thus, there was a steady increase in the level of blood lymphocytes by the 10th day of the postoperative period in all groups, on average by 8.95% ( $p = 0.000$ ), by 10.35% ( $p = 0.003$ ), by 10.91% ( $p = 0.000$ ) respectively.

This dynamics reflects the positive effect on the immune status of patients of the combined use of parenteral and enteral types of nutritional support in the postoperative period in this group of patients.

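### Conclusion 1 credits mixed feeding with better caloric intake, but no delivered energy or protein was listed as a measurement or reported, so the study cannot say whether any advantage comes from route or amount

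*Combined protocol and SAP*

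**What the plan says.** The protocol (I. Purpose of the study and introduction) sets out a "Comparative analysis of the degree of influence of isolated enteral, isolated parenteral and mixed type of nutritional support on the nutritional status" of patients after hepatopancreatoduodenal cancer surgery. The groups (protocol II.1, repeated in the report under Research objectives) are enteral (n=31), parenteral (n=30) and mixed (n=30). Each is defined by route only. Neither place gives an energy or protein target, a rule for equal calories across groups, or the enteral/parenteral split in the mixed group.

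The protocol's study plan (III. Methods and procedures) lists "transaminases, thymol test, urea, creatinine, study of total protein and its fraction, state of nitrogen metabolism, blood glucose level, body mass index", together with blood gases, body composition and immunological state. Under 1. Methods and procedures, the list that opens "Some nutritional status indicators available for determination at the Oncology Clinic were assessed" covers weight and body mass index, basal metabolic rate and laboratory values. Recovery outcomes follow, including "the timing of the onset of intestinal motility, the appearance of stool, the return to a normal diet". The report's Clinical research program repeats this material.

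Item 1 of the report's Conclusion opens "According to the NRI nutritional status assessment scales, the SGA mixed type of nutritional support" and says that this type of support "showed higher effectiveness in stabilizing the condition and maintaining the patients' caloric intake", in comparison with both isolated types. The Results and discussion text attributes the mixed-group finding to digestion being preserved or restored in the gut, with parallel coverage "of the required daily caloric intake by parenteral administration of mixtures".

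**The concern.** A conclusion that ranks three groups on caloric intake needs a record of what each group received. Without one, the intake part of item 1 is an assertion.

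The gap also limits how the other findings can be read. Amount fed is neither fixed by the plan nor measured, and the report's own explanation for the mixed group contains an amount component. A reader choosing between feeding methods cannot tell whether any better result in the mixed group came from combining routes, from the quantity received, or from both.

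**Working it through.** No arithmetic can test an intake claim when no intake figure exists. The check is to look for a data source in each place that could hold one.

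| Place | Content | Energy or protein prescribed or delivered? |
|---|---|---|
| Protocol, Brief Summary | Screening, body mass index, basal metabolic rate, laboratory values | No |
| Protocol II.1; report, Research objectives | Groups by route, 31 + 30 + 30 = 91 | No |
| Protocol III, study plan | Biochemistry, blood gases, body composition, immunological state | No |
| Protocol III, 1. Methods and procedures; report, Clinical research program | NRS 2002, SGA, NRI, weight, basal metabolic rate, laboratory values, gut recovery, stay, complications | No |
| Protocol, 2. Data analysis and monitoring; report, Methods of statistical data analysis | Descriptive statistics and tests | No |
| Report, Results and discussion | Malnutrition categories, basal metabolic rate, protein, lymphocytes, transaminases, bilirubin | No |

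**Nearest candidates.** Patient questioning within the screening methods, nitrogen metabolism and return to a normal diet come closest. None is defined as delivered energy or protein. The last two have no reported result, and the screening scales are reported as malnutrition categories.

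**The kcal figures.** Results and discussion gives end-of-support basal metabolic rate as 2500.1 ± 353.4 (enteral), 2350.0 ± 330.5 (parenteral) and 2250.0 ± 105.2 (mixed) kcal/day, the last described as a fall of 6.78%.

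- Implied mixed-group starting value: 2250.0 / (1 − 0.0678) = 2413.6 kcal/day.
- Implied fall: 2413.6 − 2250.0 = 163.6, about 164 kcal/day.
- The all-group fluctuation of 335.89 kcal/day, given as 13.44%, implies a base of 335.89 / 0.1344 = 2499.2 kcal/day.

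All of these are on the scale of basal metabolism, which the protocol says is "calculated using the Harris-Benedict equation, based on anthropometric data of the patient (gender, age, weight and height". Over about two weeks sex and height are fixed and age effectively so. Weight is therefore the only listed input that can move. Nothing received by tube or infusion enters the formula, so neither the fall nor its p-value (p < 0.03) shows how many calories any group was given. The report's inference from this fall to better-covered energy costs, repeated in Conclusion item 3, has the same gap.

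**Route and amount.** Route is fixed by group. Amount is neither fixed nor recorded, and the report invokes it for the mixed group. The two components cannot be separated with the listed data.

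**The case against.** The strongest reply is that this is a comparison of feeding strategies. The stated purpose compares types of support, and the scientific hypothesis speaks of different approaches to delivering nutrients. Neither claims an effect of route at equal amount. If mixed feeding works because it delivers more when the gut is impaired, that is part of how the strategy works. This stands, and it is why the fix asks for strategy wording and not for a route effect. It does not supply a source for the intake statement.

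A second reply is that the report does give a basis: NRI and SGA for item 1, and basal metabolism for energy coverage. That is true, but neither is a record of intake. The English also reads as a translation, so the phrase may be looser than intended. If so, rewording it costs little.

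Three stronger readings are tempting, and the documents support none of them:

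- A reader might infer that mixed-group patients received more than the others. The report is silent on calories delivered to the enteral group, and silence does not show a shortfall. The same text describes digestion preserved or restored in spite of intestinal paresis, and the paresis argument does not reach the parenteral group at all.
- A reader might take the basal-metabolism values as energy requirements and work out a calorie gap. Any such gap would only restate an assumed delivery percentage, since the documents give none.
- A reader might conclude that the preferred feeding method would change. For a comparison of strategies that does not follow.

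**Conclusion.** The concern holds in a limited form. The caloric-intake part of Conclusion item 1 has no intake measurement behind it, and the study cannot say whether any advantage of mixed feeding comes from route or from amount. Whether the amounts differed is unknown, so no size can be attached to a difference.

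No printed number or test result changes. What changes is what a headline conclusion can claim.

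This rests on the measurement and results text in the public document. Some pages and figures are not available, and the individual items of the screening scales are not described.

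**What to change.** The protocol's study plan already begins with a content analysis of medical documentation. It does not say whether those records hold daily feeding or infusion amounts, so establish that first.

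- **If they do:** extract delivered kcal and protein per patient-day, by route, for the support period. Tabulate them by group ahead of the outcomes, and base any intake statement on that table.
- **If they do not:** delete the caloric-intake wording from Conclusion item 1, limit the item to the NRI and SGA categories observed, and state unmeasured delivery as a limitation.
- **In either case:** describe the comparison as one of feeding strategies, meaning route plus amount received. Similar group averages would not by themselves establish a pure route effect, because amount delivered arises after patients enter their groups. Check the energy-coverage statements in Results and discussion and in Conclusion item 3 against the same standard.

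The cost is chart abstraction for 91 patients and one table, or an edit to the conclusion. The downside is a narrower claim.

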### Research objectives:

1. To conduct a comparative assessment of the dynamics of nutritional deficiency and nutritional status of patients operated on for malignant tumors of the hepatopancreatoduodenal zone in the early postoperative period during isolated enteral, isolated parenteral and mixed types of nutritional support.
2. To analyze the dynamics of the state of protein and carbohydrate metabolism, the consistency of liver function in cancer patients operated on for malignant tumors of the hepatopancreatoduodenal zone, against the background of isolated enteral, isolated parenteral and mixed type of nutritional support in the early postoperative period.
3. To determine the degree of effectiveness of these methods of nutritional support in this category of patients based on the totality of the results of assessing nutritional status and the dynamics of the level of basal metabolism in these patients in the early postoperative period.

Researched 91 patients, will be divided into 3 groups:

1. The first group (n=31) included patients who received enteral nutrition (EN) after surgery.
2. The second group (n=30) included patients receiving parenteral nutrition (PN).
3. The third group (n=30) receiving mixed nutrition (MN), as is commonly considered the method of partial parenteral nutrition, in the early postoperative period.

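### Conclusion 2 claims relatively constant total protein in every patient; the report's own results neither support this nor agree with it

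*Combined protocol and SAP*

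**What the plan says.** All of the text is in the report part of the combined document.

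- **Conclusion, item 2.** Over the whole period of enteral, parenteral and mixed support, "all patients (100%) showed a relatively constant level of total blood protein". This is the only conclusion on protein.
- **Results and discussion, day 5.** The mean fall from baseline is put at 6.8 ± 0.95%. The sentence that carries this figure speaks of a "gradual decrease in the level of total blood protein by the 5th day of the postoperative period, on average, by" (the figure comes next). The authors attribute the fall to catabolism and continuing protein losses. The ± is not labelled.
- **Results and discussion, later course.** The fall was followed by a rise, described as coming "with a fairly significant increase by the end of nutritional support". Its size is not given.
- **Results and discussion, by arm.** The report says that "a statistically significant increase in the level of total blood protein was noted in the mixed nutrition group" (p = 0.004). For the enteral and parenteral arms, "differences in the dynamics of total protein levels were found at the level of a statistical trend", with p = 0.108 and p = 0.129 respectively.
- **Research objectives, objective 2.** Protein metabolism is a named objective, to be compared across the three types of support.

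Neither the protocol's Data analysis and monitoring section nor the report's Methods of statistical data analysis defines relative constancy of a laboratory value. Neither plans a count of patients who meet such a definition. Both describe group summaries, group tests and correlations.

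**The concern.** Item 2 is a statement about individuals: every patient, in every arm, throughout. The results are statements about group means: down by day 5, up by the end, with a significant rise in one arm. The conclusion cannot be derived from those results, and its overall message is not theirs.

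The comparison of three arms is the purpose of the study, and protein is part of objective 2. Someone who reads only the Conclusion learns that protein hardly moved and that the arms were alike. Someone who reads the Results learns of a fall, a recovery and a significant rise under mixed nutrition. The two readers leave with different answers to the same objective. A new test between arms would not cure this while the sentence in item 2 stands.

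**Working it through.** **The plan's own figure.** The 100% cannot be reproduced. That would need a cut-off and patient-level changes in total protein, and the documents give neither. What can be checked is whether the published summary makes 100% plausible, and for which cut-offs.

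**Inputs**

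- Mean fall by day 5: 6.8%, with ± 0.95 (Results and discussion).
- Number of patients: 91, in arms of 31, 30 and 30 (Research objectives). That the ± refers to all 91 is my assumption; the text speaks of the groups together.
- Meaning of ±: the report's methods list "the calculation of the arithmetic mean (M) with error (m) and 95% confidence interval (95% CI), standard deviation (s"), so the mean is paired with an error m and the standard deviation is a separate item. That points to a standard error. The protocol's Data analysis and monitoring section lists only a standard deviation, so I keep both readings.
- Assumption: individual percentage changes are normally distributed.

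**Reading A: 0.95 is a standard error**

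- z = 6.8 / 0.95 = 7.2
- 95% CI for the mean fall = 6.8 ± 1.96 × 0.95 = 4.9% to 8.7%
- Implied SD = 0.95 × √91 = 9.06%
- Share changing by more than c in either direction = 1 − Φ((c − 6.8)/9.06) + Φ((−c − 6.8)/9.06)

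**Reading B: 0.95 is a standard deviation**

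- Share falling by more than c = 1 − Φ((c − 6.8)/0.95); rises beyond c are negligible here.

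| Limit c | Reading A (SD 9.06%) | Reading B (SD 0.95%) |
|---|---|---|
| 5% | 0.675 | 0.971 |
| 10% | 0.394 | 0.0004 |

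Under reading B at 10%, the expected number outside the limit is 91 × 0.0004, or about 0.03 patients. If the standard error in reading A refers instead to one arm of 30, the SD is 0.95 × √30 = 5.20% and the shares are 0.647 at 5% and 0.270 at 10%.

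At a 5% limit, 100% constancy is implausible under every reading. At a 10% limit it is implausible under reading A and plausible at day 5 under reading B. These cut-offs are mine; the documents give none.

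**The later rise.** No size is reported, so only the p-values can be used. I read them as within-arm tests of change, with a two-sided normal approximation:

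- Mixed: p = 0.004 gives z = 2.88, a mean change of 2.88/√30 = 0.53 SD.
- Enteral: p = 0.108 gives z = 1.61, and 1.61/√31 = 0.29 SD.
- Parenteral: p = 0.129 gives z = 1.52, and 1.52/√30 = 0.28 SD.

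If the SD of change is the same in each arm and all three changes are rises, the differences between arms are:

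- Mixed minus enteral: (0.53 − 0.29) / √(1/30 + 1/31) = 0.24 / 0.256 ≈ 0.9
- Mixed minus parenteral: (0.53 − 0.28) / √(1/30 + 1/30) = 0.25 / 0.258 ≈ 1.0

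Both are well below 1.96. This is only illustrative, but it shows that one significant and two non-significant within-arm results need not mean that the arms differ.

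**The case against.** The best defence is the qualifier: item 2 says relatively constant, not unchanged. The Results themselves call the fall slow and gradual and report that it was followed by a rise. Two of the three arms show no significant change. The reference point of the mixed-arm p = 0.004 is not stated; if it is the day-5 low, a dip of about 7% and a recovery may leave little net movement. If 0.95 is a standard deviation, almost every patient would lie within a 10% band at day 5.

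Much of this stands. A reader might infer that the Results disprove item 2 outright. They do not: a significant change in a mean does not show that each patient changed, p = 0.004 carries no size, and no limit exists against which to fail the claim. For the enteral and parenteral arms, the conflict rests on the fall and rise described for the groups together, not on their own p-values.

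The defence still does not supply what item 2 asserts. It needs a cut-off that the report never states and a count that it never gives, and the qualifier does not cover the omission of the one significant protein result.

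**Conclusion.** Wrong as written. The statement that 100% of patients had relatively constant total protein is unsupported, because there is no definition and no count. It is also inconsistent with the reported fall, the later rise and the significant mixed-arm result. The most direct conflict is with the rise and p = 0.004; the day-5 fall adds to it.

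As to size, the share of patients changing by more than 5% at day 5 is about 68% on the standard-error reading and 97% on the standard-deviation reading. Beyond 10% it is about 39% or almost none. These figures rest on normality, on n = 91 and on limits that are not the report's. They show that the 100% depends on an unstated cut-off; they do not disprove it for every cut-off.

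A reader might also infer from the three p-values that mixed nutrition raised protein more than the other two types. The documents do not support that either, since no direct comparison between arms is reported for total protein.

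**What to change.** Rewrite item 2 of the Conclusion:

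1. Remove the claim about all patients (100%) and the wording on relative constancy.
2. Give, for each arm, the mean change in total protein from the preoperative value with its 95% CI at day 5, day 10 and the last measured time point of support. Name that last point: the report puts the end of support at days 10–15 in the Results on basal metabolism and at days 15–20 in Conclusion item 3, and item 2 covers the entire period.
3. State whether the mixed-arm p = 0.004 is measured from the preoperative or the day-5 value, and label every ± as a standard error or a standard deviation.
4. Claim a difference between arms only from a direct between-arm comparison adjusted for the preoperative value, with its CI.

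The cost is a change of wording and a small re-run of data already collected. The conclusion becomes less tidy, and it may no longer be possible to say anything firm about differences between the arms.
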